We will conduct an observational pre/post study to evaluate the impact of these efforts to optimize oxygen delivery and oxygenation in critically ill trauma patients.

Hypotheses:

[figure not shown]
We hypothesize that the clinical efforts to improve adherence to oxygen guidelines will:

- a) improve the proportion of time spent with target normoxia thresholds (oxygen saturation [SpO_2] 90-96%) by
- b) reducing utilization of unnecessary supplementation oxygen
- c) without a substantive increase in hypoxic episodes or an adverse impact on clinical outcomes.

II. Background and Significance:

Oxygen therapy has undisputed importance in the care of critically ill medical and trauma patients to treat and prevent morbidity associated with hypoxia.^{1,2} However, generous supplemental oxygen is routine, and often results in hyperoxia.³⁻⁶ While there is no known benefit of excessive oxygenation, common clinical perception has been that this practice is safe and creates a margin of safety against hypoxia.⁷⁻⁹ However, evidence indicates that hyperoxia can also harmful. Here we summarize the rationale and relevance of the proposed research to avoid but hypoxia and hyperoxia and target normoxia.

[figure not shown]
Pre-clinical and observational data support the concept of targeted normoxia. There is a U-shaped relationship between oxygenation and mortality in critically ill patients, with both ends of the spectrum—hypoxia and hyperoxia—individually associated with higher mortality.^{10,11} Laboratory evidence has long demonstrated toxicity associated with hyperoxia through mitochondrial production of pro-inflammatory reactive oxygen species

ischemic vasoconstriction that leads to tissue damage and vital organ injury.¹²⁻¹⁴ **Figure 1** summarizes the underlying cellular mechanisms for balance between the beneficial and harmful effects of oxygen therapy.

Figure 1. Beneficial (green arrows) and deleterious (red arrows) effects of oxygen therapy during circulatory shock. *Adapted from Asfar P et al. Intensive Care Med 2015;41:1118.*

[figure not shown]
Numerous observational cohort studies have demonstrated an association between hyperoxia and higher mortality broadly in intensive care unit patients and in specific subpopulations, such as cardiac arrest, myocardial infarction, ischemic stroke, and

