patients, supplemental include fraction of inspired oxygen (FiO_2), positive end expiratory pressure, ventilator mode, mean airway pressure, and tidal volume. With this information we can calculate both P/F ratio and oxygenation index. For non-ventilated patients, we will collect volume and route of supplemental oxygen. These data will be used to longitudinally calculate the observed oxygenation compared to the defined oxygenation targets (SpO_2 90-96% and PaO_2 60-100 mmHg). In addition, we will calculate the duration of hyperoxia time ($\text{SpO}_2 > 96\%$ or $\text{PaO}_2 > 100$ mmHg, unless no supplemental oxygen is delivered), and number/duration of hypoxia episodes ($\text{SpO}_2 < 88\%$ or $\text{PaO}_2 < 60$ mmHg, unless FiO_2 is 100%).

Although this pilot study will be underpowered for clinical outcomes, we will measure in-hospital mortality, ventilator-free days, duration of supplemental oxygen, acute organ injury (as measured by daily Sequential Organ Failure Assessment [SOFA] scores over 7 days), intensive care unit length of stay, hospital length of stay, and hospital disposition (facility vs. home).

B. Description of Population to be Enrolled and C. Study Design and Research Methods

We will conduct a pilot study to inform a future larger scale implementation study across multiple trauma centers to test the clinical effectiveness of the targeted normoxia strategy. In the proposed pilot study, we will test and optimize feasibility and potential for effectiveness.

Study Design and Setting: This study will be an observational before-after study conducted at the University of Colorado Hospital.

Participants: We will compare oxygenation and outcomes trauma patients admitted to the ICU during the 6 months after the clinical implementation to similar patients during the same 6 months in the prior year (to adjust for seasonal effects) and the immediate preceding 6 month period (to minimize potential for secular trends).

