The clinical implementation of normoxia guidelines is part of standard care and therefore there is no specific research intervention. While the research team will help the clinical leadership with education of clinical staff, the research team will have no interactions with patients or surrogates. Patient care will occur per treating clinicians, including decisions on when to adhere and not to adhere to the guidelines on normoxia. The research procedures will be observational, retrospective data collection. We will collect data on patients with acute injury that are admitted from the emergency department to the surgical-trauma or neurosurgical intensive care units.

D. Description, Risks and Justification of Procedures and Data Collection Tools:
The risks of this research are related to retrospective data collection and interviews as below.

Identifiers

Human subjects will be identified based on the unique hospital encounter number that is specific to the exact hospitalization for an individual patient. Additional identifiers will be temporarily collected (medical record number and date of birth) to ensure proper matching for electronic data collection and to facilitate manual chart review when needed. These identifiers will be removed from the dataset as soon as the database is cleaned and closed for analysis (thereby creating a completely de-identified dataset thereafter).

Confidentiality

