Electronic data will be stored on University servers or on password-protected/encrypted computers that are behind the University firewall. We do not anticipate any hard copy data, but should be generated, they will be secured in a locked file cabinet in a locked office. Data will be stored for as long as IRB and DOD regulations recommend, whichever is longer (typically 5 years). A limited de-identified dataset will be archived long-term for future use by the local investigators and the general research community. The proposed research does not interface with the FDA, and thus, there are no special requirements relating to disposition of data.

E. Potential Scientific Problems:

The biggest challenge to the research will be the extent to which guideline adherence is improved during the study period.

There can also be challenges with electronic data collection with Health Data Compass. However, we have worked closely with Compass in the preparatory work (COMIRB #17-1359), and also will supplement electronic data collection with manual chart review as needed.

F. Data Analysis Plan:

We will model continuous SpO₂ and PaO₂ data separately and a third model where both are combined. The SpO₂ model will have the most field relevance but incorporating the PaO₂ data will be useful in applying results to the hospital setting in future implementation trials. Specific attention will be paid to the defined normoxia target range, as well as short-term episodes of hypoxia or hyperoxia. Oxygenation and oxygen supplementation data will be analyzed descriptively.

Clinical outcomes will be analyzed descriptively to compare the pre- and post-periods. We will also adjust for a limited number of covariates (eg, injury severity) to reduce risk of confounding. However, we fully recognize that the primary purpose of this pilot intervention is feasibility and safety, and so clinical outcomes will be underpowered.

G. Summarize Knowledge to be Gained:

The proposed pilot study will help us to understand the feasibility, barriers, and facilitators for improving oxygenation practices in critically ill trauma patients. The results will provide valuable preliminary data for planning a large multicenter implementation trial to evaluate the impact of this intervention on clinical outcomes and safety. These data collectively will provide actionable data to improve care of critically injured civilians and military service members.

H. References:

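### Hospice discharges are invisible in the mortality and disposition outcomes, so a change in hospice use between periods would bias the mortality comparison in either direction

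*Combined protocol and SAP*

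**What the plan says.** Research Methods, section A (Outcome Measure(s)) lists the clinical outcomes: "we will measure in-hospital mortality, ventilator-free days, duration of supplemental oxygen, acute organ injury", then the SOFA detail, then "intensive care unit length of stay, hospital length of stay, and hospital disposition (facility vs. home". Mortality has no fixed-day horizon. Disposition has two levels, and neither hospice nor death is given a place. Ventilator-free days are named once, without a window or a scoring rule.

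Section D (Identifiers) ties each subject to a "unique hospital encounter number that is specific to the exact hospitalization for an individual patient". The design section says that "the research team will have no interactions with patients or surrogates" and that data collection is retrospective. No vital status after discharge is planned. Section D also says that identifiers are removed once the database is cleaned and closed.

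Section F (Data Analysis Plan) says: "Clinical outcomes will be analyzed descriptively to compare the pre- and post-periods". It allows adjustment for a few covariates such as injury severity. Sections A and F both describe the clinical outcomes as underpowered. Hypothesis (c) in section I nevertheless expects the guideline effort to work "without a substantive increase in hypoxic episodes or an adverse impact on clinical outcomes".

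**The concern.** Moving a dying patient to hospice changes where the death occurs. Under this plan it also changes the recorded outcome, from a death to a live discharge. The two-level disposition then hides the change, because the patient joins everyone else sent to a facility or home.

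This matters here because the periods are not randomised. Three six-month periods are compared, together spanning 18 months (3 × 6), and discharge practice could change over that time for reasons unrelated to oxygen. If hospice use rises, in-hospital mortality falls with no change in how many patients are dying, which would be read as support for hypothesis (c). If it falls, the guideline effort could look harmful when it is not. Adjusting for injury severity balances the patients being compared; it does not reclassify an outcome recorded differently in the two periods.

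**Working it through.** **Inputs.** The documents give no sample size, death rate, hospice rate, margin or test for clinical outcomes, so there is no plan figure to reproduce. All rates below are assumptions, shown over a range.

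**Formula.** Let D be the proportion who die in hospital or are discharged to hospice, and h the share of those who are hospice discharges. Then:

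- recorded in-hospital mortality = D × (1 − h)
- recorded difference = D_post × (1 − h_post) − D_pre × (1 − h_pre)
- artefact = recorded difference − (D_post − D_pre) = D_pre × h_pre − D_post × h_post

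The artefact is therefore the change in the hospice discharge rate with its sign reversed.

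**No true difference (D equal in both periods).**

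| D | h pre | h post | Recorded pre | Recorded post | Artefact (points) |
|---|---|---|---|---|---|
| 10% | 10% | 10% | 9.0% | 9.0% | 0 |
| 10% | 10% | 20% | 9.0% | 8.0% | −1.0 |
| 10% | 10% | 30% | 9.0% | 7.0% | −2.0 |
| 10% | 20% | 10% | 8.0% | 9.0% | +1.0 |
| 20% | 10% | 10% | 18.0% | 18.0% | 0 |
| 20% | 10% | 20% | 18.0% | 16.0% | −2.0 |
| 20% | 10% | 30% | 18.0% | 14.0% | −4.0 |
| 20% | 20% | 10% | 16.0% | 18.0% | +2.0 |

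**True rise of 3 points (D from 10% to 13%).**

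- Share constant at 10%: 13 × 0.9 − 10 × 0.9 = 11.7 − 9.0 = +2.7 points, so the difference is only slightly shrunk.
- Share from 10% to 30%: 13 × 0.7 − 10 × 0.9 = 9.1 − 9.0 = +0.1 point, so the rise is almost hidden.
- Share from 20% to 10%: 13 × 0.9 − 10 × 0.8 = 11.7 − 8.0 = +3.7 points, so the rise is overstated.

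**Against sampling error.** With an assumed 100 to 300 patients per period and 10% mortality, the standard error of a difference between two periods is √(2 × 0.10 × 0.90 / n). That is 4.2 points at n = 100 and 2.4 points at n = 300. The 2-point artefact at D = 10% is therefore about 0.5 to 0.8 of a standard error (2/4.2 and 2/2.4).

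**The case against.** The strongest case against giving this weight is that the clinical outcomes are descriptive, are declared underpowered, and carry no test, margin or decision rule that a misclassified death could overturn. The primary outcome is oxygenation over the first 7 days. The illustrated 2-point artefact is smaller than one standard error. The plan also includes the immediately preceding six months as a comparator specifically to limit secular trend.

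Most of this stands, and it limits the weight of the point. It does not remove it. Low power is imprecision, whereas a shift in hospice use is bias, which more patients would not reduce. The adjacent comparator narrows the time gap but cannot show whether hospice use changed, because hospice is not recorded. Hypothesis (c) still draws on these outcomes, and section G says the results will inform a larger trial of clinical outcomes and safety.

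A reader might infer two stronger claims, which the documents do not support.

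- **Patients transferred on a ventilator are scored as ventilator-free.** The plan states no such rule. It names "ventilator-free days, duration of supplemental oxygen" and leaves the window, and the handling of death and of discharge on a ventilator, undefined. That scoring is one possible reading only.
- **Disposition is also flawed because it stops at discharge.** Disposition is by nature fixed at discharge. A ventilated transfer, or a discharge to inpatient hospice, would fall under facility, the less favourable level, so it would not flatter the result. The gap is that "hospital disposition (facility vs. home" gives hospice and death no place of their own.

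**Conclusion.** The concern holds for mortality, and for disposition only in that it cannot identify hospice discharges. Absent a special rule, a patient discharged to hospice counts as a survivor. The mortality comparison is biased if the hospice share differs between periods, and the direction depends on which way it moves. With a constant share and no true difference the bias is zero; a constant share alongside a true difference only scales it slightly (3.0 to 2.7 points in the example).

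The size rests wholly on assumed rates: 0 to 4 points for D of 10% to 20% and a share going from 10% to between 10% and 30%, with the opposite sign if the share falls. The documents hold no data on discharge practice, so it would be wrong to conclude that the bias is present, or that it favours the post-period. Ventilator-free days need a definition, but that is missing detail and not a demonstrated bias.

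**What to change.** In section A:

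1. Keep in-hospital death, and report *in-hospital death or discharge to hospice* beside it, by period.
2. Record disposition with separate levels for hospice and for death, alongside facility and home, and tabulate hospice discharges by period.
3. Do this before the database is closed and identifiers are destroyed. If only facility or home has been stored by then, hospice discharges cannot be recovered from the chart.
4. As a clarification only, state the ventilator-free-day window and how death and discharge on a ventilator are scored.

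The cost is a change of outcome wording and one more discharge field to abstract. Section D already plans manual chart verification, though it does not list hospice as an item. The downside is that some hospice patients survive for a time, so the combined row overstates early deaths; the in-hospital death row beside it shows how much of the total is hospice discharge. The primary oxygenation analysis needs no change.

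### Daily SOFA includes a respiratory part computed from the oxygen quantities the programme changes, so a SOFA score without that part should be compared alongside the total (low severity)

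*Combined protocol and SAP*

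**What the plan says.** Section III.A, Outcome Measure(s), lists acute organ injury among the clinical outcomes and measures it by "daily Sequential Organ Failure Assessment [SOFA] scores over 7 days". It gives no component scores, no rule for total against sub-score, and no summary over the seven days. Because nothing is separated or excluded, the total score is the natural reading, although the word "total" is not used.

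The hypotheses in section I state what the programme is meant to change: "improve the proportion of time spent with target normoxia thresholds" by "reducing utilization of unnecessary supplementation oxygen". Section III.A sets the targets at SpO2 90-96% and PaO2 60-100 mmHg. It defines hyperoxia as SpO2 above 96% or PaO2 above 100 mmHg while on supplemental oxygen. For the ventilator data it says "With this information we can calculate both P/F ratio and oxygenation index".

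The third hypothesis expects this to happen "without a substantive increase in hypoxic episodes or an adverse impact on clinical outcomes". Section F, Data Analysis Plan, says "Clinical outcomes will be analyzed descriptively to compare the pre- and post-periods", with adjustment for a limited number of covariates such as injury severity. Neither section mentions that the oxygen targets and the SOFA respiratory inputs overlap.

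**The concern.** An outcome meant to show whether organs are injured should not be built from the quantity the programme manipulates. The ratio PaO2/FiO2 is not a constant of the lung: with shunt and gas exchange held fixed, it changes as FiO2 changes. A programme that lowers FiO2 and PaO2 can therefore change the respiratory points, and so total SOFA, with no change in any organ.

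What is at stake is the reading of the third hypothesis. SOFA is the only listed measure of acute organ injury. A pre/post difference in the total could be taken as protection or harm when part of it is arithmetic, or a real difference could be masked. Adjusting for injury severity does not remove the effect, because it arises from the exposure itself. The pilot is also meant to inform a larger multicentre study, which could inherit the misreading.

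**Working it through.** The documents give no SOFA effect, standard deviation, sample size or FiO2 distribution, so there is no figure of the plan's own to reproduce. The check asks whether the score can move when only FiO2 moves.

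**Inputs from the protocol:** targets SpO2 90-96% and PaO2 60-100 mmHg; hyperoxia defined as SpO2 above 96% or PaO2 above 100 mmHg.

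**Assumptions not in the protocol:** SOFA respiratory cut-points at P/F below 400, 300, 200 and 100 for 1, 2, 3 and 4 points (3 and 4 only with respiratory support); haemoglobin 10 g/dL; PaCO2 40 mmHg; respiratory quotient 0.8; barometric pressure 760 mmHg; shunt fraction s and arteriovenous oxygen difference D as shown.

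**Formulas:**
- Alveolar PO2: PA = FiO2 × (760 − 47) − 40/0.8 = 713 × FiO2 − 50.
- Saturation (Severinghaus): S(P) = 1 / (1 + 23400/(P³ + 150P)).
- Oxygen content (mL/dL): C(P) = 1.34 × 10 × S(P) + 0.0031 × P.
- Arterial content: Ca = C(PA) − D × s/(1 − s). Solve C(PaO2) = Ca for PaO2, then P/F = PaO2/FiO2.

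The content deficit D × s/(1 − s) is 4.5 × 0.20/0.80 = 1.125 for lung A and 4 × 0.15/0.85 = 0.706 for lung B.

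| Lung | FiO2 | PA | C(PA) | Ca | PaO2 | SpO2 | P/F | Points |
|---|---|---|---|---|---|---|---|---|
| A: s 20%, D 4.5 | 0.50 | 306.5 | 14.34 | 13.21 | 86.8 | 96.6% | 174 | 3 |
| A | 0.30 | 163.9 | 13.84 | 12.71 | 68.1 | 93.3% | 227 | 2 |
| B: s 15%, D 4 | 0.70 | 449.1 | 14.79 | 14.08 | 228.7 | 99.8% | 327 | 1 |
| B | 0.60 | 377.8 | 14.57 | 13.86 | 169.0 | 99.5% | 282 | 2 |
| B | 0.30 | 163.9 | 13.84 | 13.13 | 82.5 | 96.1% | 275 | 2 |

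Each starting row (A at 0.50, B at 0.70 and B at 0.60) is hyperoxic by the protocol's definition. Each end row is in target, taking SpO2 in whole per cent for lung B. The lung does not change, yet:
- A, 0.50 to 0.30: 3 to 2 points, an apparent improvement.
- B, 0.70 to 0.30: 1 to 2 points, an apparent worsening.
- B, 0.60 to 0.30: 2 points at both, no change.

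**Sensitivity.** The P/F values shift by a few units with the choice of constants. With a solubility of 0.0030 they become 171 to 226 for A and 317 to 274 for B (0.70 to 0.30), and the scores are unchanged. At 630 mmHg with D = 4, both directions again occur. At 20% shunt, FiO2 0.60 to 0.30 gives P/F 155 to 220 (3 to 2 points). At 10% shunt, 0.70 to 0.30 gives 317 to 284 (1 to 2 points).

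**How often a cut-point is crossed.** An unweighted grid at 760 mmHg (shunt 2-35%, haemoglobin 10-12, D 4-5) was limited to lungs that start hyperoxic and end at SpO2 of about 90% or more.

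| FiO2 step | Score unchanged | Falls | Rises |
|---|---|---|---|
| 0.40 to 0.30 | 87% | 9% | 4% |
| 0.50 to 0.40 | 79% | 10% | 11% |
| 0.60 to 0.40 | 70% | 7% | 23% |
| 0.70 to 0.30 | 40% | 29% | 31% |

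These are shares of a grid, not of patients.

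**The case against.** The strongest reply is that little rests on SOFA and that no net bias has been shown. SOFA is one of seven clinical outcomes. The protocol calls them underpowered and plans to describe them, and it states no SOFA test, threshold or decision rule. For modest FiO2 steps most grid cells do not cross a cut-point, and those that do go both ways. All of this stands and sets the severity. It does not remove the point: the third hypothesis still speaks of clinical outcomes, and low power is no reason to keep an avoidable artefact.

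Four stronger readings are tempting, and the documents do not support them.

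- *A reader might infer that total SOFA is biased in a known direction.* It is not: lungs A and B move in opposite ways. Without the FiO2 distribution, the shunt distribution or the spread of SOFA, the effect on a period mean cannot be given a sign or size.
- *A reader might illustrate the effect with a step from 0.40 to 0.30.* At 20% shunt (D 4.5) this takes P/F from 191 to 227, and at 25% from 164 to 201, each crossing a cut-point. But those patients start at SpO2 of about 95% and 92%, already in target, so they are not the ones the programme is aimed at.
- *A reader might infer that availability of the component differs between periods,* because "For non-ventilated patients, we will collect volume and route of supplemental oxygen" and no conversion to FiO2 is given. The missing rule is real. But that sentence describes data for the oxygenation outcome, the protocol also allows manual chart review, and nothing shows a difference between periods.
- *A reader might conclude that total SOFA should be replaced.* That would take the lung out of the organ-injury measure in a study of oxygen, and it would drop the named score for a modified one. The documents do not require that trade.

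**Conclusion.** The point holds in a limited form. Daily SOFA, read as the total, contains a component computed from quantities the programme deliberately changes, and the plan does not deal with this. In an unchanged ventilated lung, titrating a hyperoxic patient to target moved the score by at most 1 point per day in the cases worked here, in either direction, and often not at all.

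This rests on the standard SOFA respiratory definition and on a fixed-shunt model whose inputs are not in the documents. It shows that the score can move, not that the period means will differ. The net effect cannot be quantified from the documents. Severity is low: this is a cheap improvement to a secondary, descriptive measure, and the primary oxygenation outcome is untouched.

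**What to change.** Keep total daily SOFA and add to sections III.A and F, in words such as: SOFA will also be calculated without the respiratory component and compared between periods; the respiratory component will be reported separately; any statement about non-respiratory organ injury under the third hypothesis will rest on the non-respiratory score.

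The cost is a line or two of text and one extra summary. No new data are needed, because the component scores must exist before the total can be formed. The small downside is that the non-respiratory score says nothing about the lung, which the total and the separately reported component still show. The non-respiratory score is free of this direct arithmetic effect by construction. It is not thereby free of the confounding that any before-after comparison carries, so the planned covariate adjustment should apply to it as well.

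### Does the analysis plan need a calendar-time term, or a rule against pooling, because its two control periods cannot together remove both trend and season?

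*Combined protocol and SAP*

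**What the plan says.** Under III.B/C, the Participants paragraph sets trauma ICU patients from the half-year following implementation against "similar patients during the same 6 months in the prior year (to adjust for seasonal effects) and the immediate preceding 6 month period". The second control is there "to minimize potential for secular trends". The sentence covers oxygenation as well as clinical outcomes. The same section gives the study's role: "We will conduct a pilot study to inform a future larger scale implementation study across multiple trauma centers".

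The Data Analysis Plan (III.F) does not mention the two controls again. On oxygenation it plans SpO₂, PaO₂ and combined models and adds: "Oxygenation and oxygen supplementation data will be analyzed descriptively." On clinical outcomes: "Clinical outcomes will be analyzed descriptively to compare the pre- and post-periods." On adjustment: "We will also adjust for a limited number of covariates (eg, injury severity) to reduce risk of confounding." It also states that "the primary purpose of this pilot intervention is feasibility and safety".

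The Specific Aim is worded more strongly: "We will conduct an observational pre/post study to evaluate the impact of these efforts".

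**The concern.** Two control periods are set up for two different threats, and the analysis section then reads as if there were one pre-period. It names no month, period or season term, and for oxygenation it does not restate any between-period contrast. An analyst working from III.F alone could merge the two controls. That would undo the seasonal match which is the reason for having the prior-year period.

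Even with the controls kept apart, neither comparison is free of both threats. Background drift towards lower oxygen use could then be reported as an effect of the education effort and carried into the planning of the larger study. If the two comparisons disagreed, the choice between them could be made after seeing the data.

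**Working it through.** **Inputs.** The plan states no sample size, power, trend or seasonal figure, so there is no number of its own to reproduce. I take months 1–6 as the prior-year control, 7–12 as the preceding control and 13–18 as the post period. That the blocks adjoin is implied by the Participants paragraph but not stated. Midpoints are 3.5, 9.5 and 15.5. Let b be a linear trend per month, S the seasonal difference (post and prior-year months minus preceding months), and assume no program effect.

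**Bias of each contrast**

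- Post minus prior year: (15.5 − 3.5)b = 12b. A stable season cancels.
- Post minus preceding: (15.5 − 9.5)b + S = 6b + S.
- Post minus pooled controls, with weight w on the prior year: (6 + 6w)b + (1 − w)S. At w = 1/2 this is 9b + S/2.

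Removing season needs w = 1 and removing trend needs w = −1, so no weighting does both. With the program effect added there are four unknowns (level, trend, season, effect) and three period means.

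**Illustration (b and S assumed, in points of time on target)**

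| b per month | S | vs prior year | vs preceding | pooled equally |
|---|---|---|---|---|
| 0.5 | 0 | 6 | 3 | 4.5 |
| 0.5 | +4 | 6 | 7 | 6.5 |
| 0.5 | −4 | 6 | −1 | 2.5 |

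**Would stating the two contrasts separately change this?** No. The first two bias columns are the contrasts that the Participants paragraph already describes. Restating them in III.F leaves 12b and 6b + S untouched. Only the third column would be ruled out, and no section plans it.

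**Would a calendar-time model do better?** Take 18 equal monthly values, with a step at month 13 and a linear trend.

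- Precision of a single 6-versus-6 contrast relative to pooled pre/post: √[(1/6 + 1/6)/(1/6 + 1/12)] = √(4/3) = 1.155.
- Step plus linear trend: the centred sums of squares are 4 (step) and 484.5 (month), with cross-product 36. So R² = 36²/(4 × 484.5) = 0.669, the variance ratio is 1/(1 − 0.669) = 3.02, and the SE ratio is 1.74.
- Adding an annual sine/cosine pair: variance ratio 8.32, SE ratio 2.88.
- With 12 free month effects the design has rank 13 for 14 parameters, so the effect cannot be estimated.
- Block season S = 4, no trend, no effect. After regressing the step on month, its residual sum of squares is 4 × (1 − 0.669) = 1.325, and its product with the season indicator is 2. The linear step therefore reads 4 × 2/1.325 = 6.04. The harmonic version reads 3.13. The simple contrasts read 0 (prior year), 4 (preceding) and 2 (pooled).
- Gradual uptake, assumed as 10k/6 points in post month k = 1 to 6, has mean 35/6 = 5.83. The simple contrasts recover 5.83; the linear step reads 4.20 and the harmonic step 2.78.

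On a block season the linear step is worse than every simple contrast, and the harmonic step is worse than the prior-year and pooled ones. Both understate a gradual effect, which is plausible when the intervention is growing staff education (section I). A smooth sinusoidal season is the favourable case for the harmonic model (bias 0), but the linear step can still be off by up to 6.2 points either way.

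**The case for a change.** The strongest case for a change is that even a descriptive comparison needs a defined comparator, and III.F does not give one. Its wording permits pooling, which brings back half of any seasonal difference. Background drift is also credible on the document's own account: section II says that professional bodies now recommend titrating to normoxia. The Specific Aim speaks of impact, the results feed a larger study, and the remedy would cost a few sentences.

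Part of this stands. III.F is silent on how the two controls are used, and the arithmetic on what each contrast retains is correct. If someone did pool, the seasonal match would be diluted.

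What does not stand is the step from silence to defect. The Participants paragraph and III.F belong to one short document. The former attaches a separate purpose to each comparator and names oxygenation explicitly, so the natural reading is two comparisons. It promises to minimize trend, not to eliminate it. The residual trend and season are limits of a single-site before-after design, and wording in III.F cannot remove them. The covariate list is open-ended, so a time term is left unspecified and is not excluded.

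**Conclusion.** No change is needed. The two-control layout gives one comparison matched on season (12b remaining) and one closer in time (6b + S remaining). A statistician reading the Participants paragraph would report both side by side. The missing sentence in III.F is a gap in detail, and filling it would alter neither estimate. The segmented model is a debatable trade-off: 1.7 to 2.9 times the pooled SE, spurious steps of 6.0 or 3.1 points on a 4-point block season, and readings of 4.2 or 2.8 where the mean effect is 5.8.

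These figures rest on adjoining six-month blocks, equal monthly volume, a linear trend and assumed values of b and S. They show what is possible and say nothing about what is likely. The conclusion also rests on the study being what III.F says it is: a descriptive pilot concerned mainly with feasibility and safety. In that setting a before-after difference is read as an association, whichever control it is measured against.
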